Dose escalation will be paused until further evaluation by the DMC if any of the following criteria are met. If it is confirmed that a stopping criterion was met, no further dosing will take place until after submission and approval of a substantial amendment if the DMC recommends the trial can continue.

- One or more participants experiencing at least possibly related Common Terminology Criteria for Adverse Events (CTCAE) Grade ≥ 3 TEAE or CTCAE grade ≥ 3 laboratory abnormality in a single cohort.
 - All grade 3 toxicities for vital signs must be confirmed with a repeat measurement obtained within 1 hour.
 - All grade 3 toxicities for laboratory parameters must be confirmed with a repeat measurement obtained within 24 hours.
- Two or more participants experiencing at least possibly related CTCAE grade ≥ 2 TEAEs or CTCAE Grade ≥ 2 laboratory abnormalities in a single cohort.
 - All grade 2 toxicities for vital signs must be confirmed with a repeat measurement obtained within 1 hour.
 - All grade 2 toxicities for laboratory parameters must be confirmed with a repeat measurement obtained within 24 hours.
- One or more participants experiencing any at least possibly related SAE in a single cohort.

Period 2 Individual Stopping Criteria:

Dosing will be paused or discontinued (per Investigator judgment) for an individual participant at any time in the study if:

- Participant experiences any severe or serious adverse event considered at least possibly related to study drug.
- Participant experiences, in the Investigator's opinion, clinically significant hypersensitivity to WVE-006 (or placebo) administration.
- Participant has any medical condition that is judged by the Investigator to jeopardize the participant's safety if he or she continues to receive the study drug.

On discontinuation of treatment, participants will be encouraged to continue follow-up for safety per protocol. Per Investigator judgment with consultation with the Sponsor, the participant may be allowed to resume participation in the study if/when the event has resolved.

Sponsor: Wave Life Sciences UK Limited	Investigational Product: WVE-006	Developmental Phase: Phase 1	IRAS ID Number: 1008635

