4 STUDY DESIGN

4.1 Overall Study Design

This is a double-blind, placebo-controlled, single ascending dose (SAD) and multidose Phase 1 study to assess the safety, tolerability, and PK of WVE-006 in healthy participants. Participants will be randomized to WVE-006 or placebo.

Period 1 will evaluate single ascending doses of WVE-006 in up to five cohorts of up to 8 healthy participants each (3:1 active:placebo). An additional cohort (Cohort 6) may be included to evaluate concentration-QTc. Participants may be on-study for up to 12 weeks. A sentinel strategy will be employed for the first 2 participants (1 active:1 placebo) of every new dose level during the SAD portion (Period 1) and in the multiple dose portion (Period 2) of the study, with a 48-hour observation period to assess for acute safety events. The Dose Escalation Committee (DEC) and the DMC will review available data through Day 8 that will include key PK parameters and safety for each dose cohort, as well as previously accumulated safety data and available PK data, to recommend subsequent dose escalation. Additional details are provided in [Section 4.1.2](#).

Dose Escalation Stopping Criteria (Period 1):

Dose escalation will be paused until further evaluation by the DMC if any of the following criteria are met. If it is confirmed that a stopping criterion was met, no further dosing will take place until after submission and approval of a substantial amendment if the DMC recommends the trial can continue.

- One or more at least possibly related Common Terminology Criteria for Adverse Events (CTCAE) Grade ≥ 3 TEAE or CTCAE grade ≥ 3 laboratory abnormality in a single cohort.
 - All grade 3 toxicities for vital signs must be confirmed with a repeat measurement obtained within 1 hour.
 - All grade 3 toxicities for laboratory parameters must be confirmed with a repeat measurement obtained within 24 hours.
- Two or more at least possibly related CTCAE grade ≥ 2 TEAEs or CTCAE Grade ≥ 2 laboratory abnormalities in a single cohort.
 - All grade 2 toxicities for vital signs must be confirmed with a repeat measurement obtained within 1 hour.
 - All grade 2 toxicities for laboratory parameters must be confirmed with a repeat measurement obtained within 24 hours.
- Any at least possibly related SAE in a single cohort.

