10.3.4 Definitions of Adverse Event Severity and Relationship to Study Drug

10.3.4.1 Severity

The severity or intensity of an AE refers to the extent to which an AE affects the participant's daily activities. AE severity (except for injection site reactions, covered in [Section 10.6](#)) will be evaluated using the criteria outlined in National Cancer Institute (NCI)-CTCAE Version 5.0 to determine its severity. The full reference can be found at:

https://ctep.cancer.gov/protocoldevelopment/electronic_applications/docs/CTCAE_v5_Quick_Reference_8.5x11.pdf.

Table 12 NCI-CTCAE General Grading Criteria

Grade	AE Severity	Definition
1	Mild	Mild; asymptomatic or mild symptoms; clinical or diagnostic observations only; intervention not indicated.
2	Moderate	Moderate; minimal, local or noninvasive intervention indicated.
3	Severe	Severe or medically significant but not immediately life-threatening; hospitalization or prolongation of hospitalization indicated; disabling; limiting self-care.
4	Life-threatening	Life-threatening consequences; urgent intervention indicated.
5	Death	Death related to AE.

Abbreviations: AE = adverse event; CTCAE = Common Terminology Criteria for Adverse Events; NCI = National Cancer Institute.

Note: the most applicable grading criteria should be used based on the nature of the AE, and this table should be used if none of the specific criteria match the AE.

Changes in the severity of an AE should be documented in the eCRF to allow an assessment to be performed related to the duration of the event at each level of intensity.

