10.3.5 Serious Adverse Events

10.3.5.1 Serious Adverse Events Criteria

An SAE is defined as any event that results in:

- Death
- Is immediately life-threatening. A life-threatening event does not include an AE that if it had occurred in a more severe form, might have caused death.
- Requires inpatient hospitalization or prolongation of existing hospitalization
- Results in persistent or significant disability/incapacity

- Is a congenital anomaly
- Important medical events that may not result in death, be life-threatening, or require hospitalization may be considered SAEs when they, based upon appropriate medical judgment, may jeopardize the participant or may require medical or surgical intervention to prevent one of the outcomes listed in this definition. Examples of such medical events include allergic bronchospasm requiring intensive treatment in an emergency room or at home, blood dyscrasias or convulsions that do not result in inpatient hospitalization, or the development of drug dependency or drug abuse.

Any hospital admission with at least one overnight stay will be considered an inpatient hospitalization. However, emergency department visits that do not result in overnight hospitalization would only be considered an SAE if they meet other SAE criteria (e.g., important medical event). Admission to the hospital for social or situational reasons (e.g., no place to stay, long distance for hospital visits, etc.) will not be considered as meeting hospitalization criteria for defining an SAE.

Hospitalization for an elective or outpatient procedure for a pre-existing condition will not be considered as an SAE and should be captured under procedures in the eCRF. However, unexpected complications and/or prolongation of hospitalization during elective surgery/procedure should be reported as an SAE.

Serious AEs must be reported within 24 hours; any updated SAE data will also be reported within 24 hours of it being available. SAEs that occur after the final follow-up visit need not be reported unless the Investigator considers them at least possibly related to study drug.

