10.6 Appendix 6: Grading of Injection Site Reactions

Individual signs or symptoms (e.g., erythema, swelling, etc.) at the injection site reported by a participant following study drug administration will be recorded as an injection site reaction and as an AE if grade 1 or more.

Grading of Injection Site Reactions (FDA, 2007)

Local Reaction to Injectable Product	Mild (Grade 1)	Moderate (Grade 2)	Severe (Grade 3)	Potentially Life Threatening (Grade 4)
Pain	Does not interfere with activity	Repeated use of non-narcotic pain reliever >24 hours or interferes with activity	Any use of narcotic pain reliever or prevents daily activity	Emergency room (ER) visit or hospitalization
Tenderness	Mild discomfort to touch	Discomfort with movement	Significant discomfort at rest	ER visit or hospitalization
Erythema/Redness	2.5 – 5 cm	5.1 – 10 cm	>10 cm	Necrosis or exfoliative dermatitis
Induration/Swelling*	2.5 – 5 cm and does not interfere with activity	5.1 – 10 cm or interferes with activity	>10 cm or prevents daily activity	Necrosis

* Induration/Swelling should be evaluated and graded using the functional scale, as well as the actual measurement.

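### Injection site reactions are taken off CTCAE grading, but both grade-based Period 1 stopping rules count only CTCAE grades, so a related non-serious Grade 3 or 4 reaction meets no rule as written

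*Combined protocol and SAP*

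**What the plan says.** Section 10.3.4.1 sets CTCAE v5.0 as the severity scale for adverse events and then makes an exception: "AE severity (except for injection site reactions, covered in" Section 10.6. That appendix (Appendix 6) has a separate four-grade table, adapted from a vaccine toxicity scale, for pain, tenderness, erythema and induration. It also says that individual signs or symptoms at the injection site "will be recorded as an injection site reaction and as an AE if grade 1 or more".

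The Period 1 dose escalation stopping rules appear twice.

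- Synopsis (Section 1.1): the first rule begins "One or more participants experiencing at least possibly related Common Terminology Criteria for Adverse Events (CTCAE) Grade" and continues with 3 or higher. The second begins "Two or more participants experiencing at least possibly related CTCAE grade" and continues with 2 or higher.
- Section 4.1: the parallel rules begin "One or more at least possibly related Common Terminology Criteria for Adverse Events (CTCAE) Grade" and "Two or more at least possibly related CTCAE grade", with the same thresholds.

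In both places each limb covers TEAEs or laboratory abnormalities, and both kinds are qualified as CTCAE grades. The only other rule is an SAE judged at least possibly related.

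Two consequences hang on these rules. A confirmed criterion halts all dosing until a substantial amendment is approved (Sections 4.1 and 4.1.2). The MTD is the dose one step below a level at which any stopping rule was met, and it is the dose meant for Period 2 (Sections 4.1.2 and 4.3).

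**The concern.** The drug is given subcutaneously, and the protocol plainly expects local reactions: it has a dedicated grading table, extra eCRF fields for them (Section 10.3.1) and a restriction on prophylaxis against them (Section 6.10). Yet the rules that stop escalation are written in the one scale from which these reactions have been removed. No sentence in the available text says that an Appendix 6 grade counts as a CTCAE grade for stopping, and none says that these reactions are exempt.

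The two scales cannot simply be swapped. In Table 12, the general description of Grade 3 involves hospitalisation, disability or limits on self-care. In Appendix 6, erythema wider than 10 cm is Grade 3, and so is pain with "Any use of narcotic pain reliever or prevents daily activity".

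The SAE rule does not close the gap. Appendix 6 grades pain or tenderness leading to an emergency room visit as Grade 4, but Section 10.3.5.1 says that "emergency department visits that do not result in overnight hospitalization would only be considered an SAE if they meet other SAE criteria".

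The same reactions could therefore stop a first-in-human trial and fix the MTD under one reading, and do neither under the other.

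**Working it through.** The plan states no figure to reproduce: Section 9.1 says the sample size was not based on hypothesis testing. The check is mainly textual.

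**Step 1. Trace a reaction through the rules.** Take events that are at least possibly related and not serious.

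| Event | Appendix 6 grade | Literal reading | Grade-for-grade reading |
|---|---|---|---|
| Erythema over 10 cm, one participant | 3 | No rule met | First rule met |
| Pain needing a narcotic, one participant | 3 | No rule met | First rule met |
| Pain with an ER visit, no overnight stay, no other SAE criterion | 4 | No rule met | First rule met |
| Erythema of 5.1 to 10 cm, two participants | 2 | No rule met | Second rule met |

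If any of these events were serious, the SAE rule would apply under both readings.

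**Step 2. Look for a bridging sentence.** The note under Table 12 tells the investigator to pick the grading criteria that best suit the event. It governs how an event is graded, not which grades stop escalation. Section 9.3.5.1 tabulates Grade 3 or 4 TEAEs without naming a scale, but that is a reporting rule. The Period 2 individual criteria (Section 7.1.1) refer to a severe event, and Appendix 6 also labels its Grade 3 as severe, so the gap is specific to Period 1.

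**Step 3. Illustrate the difference.** A full cohort has 6 active and 2 placebo participants (Section 4.1.2). Assume independent participants and a single cohort. The rates below are assumptions.

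First rule, one or more participants at Grade 3 or higher: 1 − (1 − q)^n.

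- n = 6: q = 1% gives 1 − 0.99^6 = 5.9%; q = 2% gives 11.4%; q = 5% gives 26.5%.
- n = 8: 7.7%, 14.9% and 33.7%.

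Second rule, two or more participants at Grade 2 or higher: 1 − (1 − p)^n − n·p·(1 − p)^(n−1).

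- n = 6: p = 5% gives 3.3%; p = 10% gives 1 − 0.531 − 0.354 = 11.4%; p = 20% gives 34.5%.
- n = 8: 5.7%, 18.7% and 49.7%.

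Using n = 6 takes the placebo risk as zero; n = 8 takes it as equal to the active risk. Under the literal reading every one of these figures is 0% from non-serious reactions, by definition.

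These counts are of participants, as in the synopsis. Section 4.1 can be read as counting events. Because Appendix 6 works sign by sign, two Grade 2 signs in one participant might then be enough.

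**The case against.** The strongest reply is that grade-for-grade is the natural reading. Appendix 6 uses the same grade numbers as Table 12 and the same labels for Grades 1 to 3. It is cross-referenced from inside the severity section. A post-dose reaction is a TEAE, which is what the rules count, and Section 9.3.5.1 treats grade as a single ladder. On this view the word CTCAE in the stopping rules is shorthand. As a statement of probable intent, this stands. A reader might infer that the sponsor meant to exempt local reactions; nothing in the documents says so.

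A second reply is that the protocol has other brakes. The sentinel step requires no other safety concerns over 48 hours. The DEC and an unblinded DMC review each cohort's data through Day 8. The DMC must confirm a criterion before the amendment requirement applies. The highest dose is only the likely default for Period 2, provided all doses were well tolerated, and the committees may go lower. This also stands in part. A reader might picture severe reactions in all 6 active participants while escalation carries on. The literal rules would allow it, but the sentinel step or the Day 8 review would probably catch it, so the documents do not support treating it as a likely course. Even so, none of these brakes is a met stopping rule. Discretion does not trigger the amendment requirement and does not define the MTD.

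Third, some text is unavailable. Parts of Sections 2.3.1, 4.1.2 and 4.3 are redacted, and the DMC and DEC charters are not among the documents. Either could address the matter. The stopping rules themselves are not redacted, and they should be complete as written.

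**Conclusion.** The point holds as a gap in the wording of a first-in-human safety rule. Taken literally, any number of related, non-serious Appendix 6 Grade 3 or 4 reactions leaves every Period 1 stopping rule unmet; grade-for-grade, one is enough. The practical risk is lowered by the sentinel step, DMC confirmation and the committees' freedom to choose a lower dose, and the sponsor's intent is probably grade-for-grade. It is worth correcting because following the rule to the letter gives the less safe outcome.

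Two limits apply. The probabilities show only how far the readings can diverge. The documents give no injection site reaction rate, so a reader should not take any of them as an estimate of how often cohorts would stop. Nor do the documents imply that Grade 2 reactions must count toward the two-participant rule. Counting them catches a tolerability signal early; exempting them avoids stopping a trial for moderate local reactions. Either choice is defensible if it is stated.

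**What to change.** In both the synopsis and Section 4.1, write the first limb as *Grade ≥3 (CTCAE v5.0, or Appendix 6 for injection site reactions)*. In the Grade ≥2 limb, state explicitly either that Appendix 6 Grade 2 reactions count or that they are exempt. When making the edit, use the same counting unit, participants or events, in both places.

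The cost is a protocol amendment that changes a few words in two places. No new data are needed, because reaction details are already collected in the eCRF. The downside is that dosing may be paused for DMC review more often, particularly if Grade 2 reactions are counted.

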10.3.4.2 Relationship to Study Drug

The Investigator's assessment of an AE's relationship to study treatment is part of the documentation process. All AEs, regardless of relationship, will be recorded in the eCRF. In addition, SAEs will be reported to regulatory authorities as required by local regulation ([Section 10.3.5.4](#)).

The relationship or association of the study drug in causing or contributing to the AE will be characterized using the following classification and criteria presented in [Table 13](#).

Table 13 Guidelines for Determining the Relationship (if any) Between Adverse Event and the Study Drug

AE Relationship	Definition
Definite	This relationship suggests that a definite causal relationship exists between treatment administration and the AE, and that other conditions (concurrent illness, progression/expressions of disease state, or concurrent medication reaction) do not appear to explain the event. The event reappears or worsens if the study treatment is re-administered.
Probable	This relationship suggests that a reasonable temporal sequence of the event with treatment administration exists, and, based upon the known pharmacological action of the treatment, known or previously reported adverse reactions to the treatment or class of treatment, or judgment based on the Investigator's clinical experience, the association of the event with the study treatment seems likely. The event disappears or decreases on cessation of study treatment.
Possible	This relationship suggests that the study treatment caused or contributed to the AE, i.e., the event follows a reasonable temporal sequence from the time of treatment administration or follows a known response pattern to the study treatment but could also have been caused by alternative factors.
Unlikely Related	This relationship suggests an improbable (but not impossible) association between the study medication and the reported event.
Not Related	This relationship suggests no association between the study treatment and the reported event.

Abbreviations: AE=adverse event.

10.3.5 Serious Adverse Events

10.3.5.1 Serious Adverse Events Criteria

An SAE is defined as any event that results in:

- Death
- Is immediately life-threatening. A life-threatening event does not include an AE that if it had occurred in a more severe form, might have caused death.
- Requires inpatient hospitalization or prolongation of existing hospitalization
- Results in persistent or significant disability/incapacity

- Is a congenital anomaly
- Important medical events that may not result in death, be life-threatening, or require hospitalization may be considered SAEs when they, based upon appropriate medical judgment, may jeopardize the participant or may require medical or surgical intervention to prevent one of the outcomes listed in this definition. Examples of such medical events include allergic bronchospasm requiring intensive treatment in an emergency room or at home, blood dyscrasias or convulsions that do not result in inpatient hospitalization, or the development of drug dependency or drug abuse.

Any hospital admission with at least one overnight stay will be considered an inpatient hospitalization. However, emergency department visits that do not result in overnight hospitalization would only be considered an SAE if they meet other SAE criteria (e.g., important medical event). Admission to the hospital for social or situational reasons (e.g., no place to stay, long distance for hospital visits, etc.) will not be considered as meeting hospitalization criteria for defining an SAE.

Hospitalization for an elective or outpatient procedure for a pre-existing condition will not be considered as an SAE and should be captured under procedures in the eCRF. However, unexpected complications and/or prolongation of hospitalization during elective surgery/procedure should be reported as an SAE.

Serious AEs must be reported within 24 hours; any updated SAE data will also be reported within 24 hours of it being available. SAEs that occur after the final follow-up visit need not be reported unless the Investigator considers them at least possibly related to study drug.

10.3.5.2 Suspected Unexpected Serious Adverse Reaction

A suspected unexpected serious adverse reaction (SUSAR) is an SAE for which there is a reasonable possibility that the study drug caused the event, and this SAE has not been previously identified as an expected/listed AE. A list of expected AEs (if applicable) is provided in the current version of the IB and is considered the Reference Safety Information (RSI) for the study. Generally, the indication for which a product is intended would not be on the list of expected serious adverse reactions (SAR), but if it did occur, would not be considered “unexpected” for SUSAR reporting. As an example, a flare-up of symptoms consistent with the underlying disease under treatment that required hospitalization would constitute a SAR; however, the event would not be considered unexpected. An exception would be if the reporter believed that study drug worsened the underlying condition.

10.3.5.3 Serious Adverse Event Follow-up

Appropriate remedial measures should be taken by the Investigator using his/her best medical judgment to treat the SAE. These measures and the participant’s response to these measures should be recorded. All SAEs, regardless of relationship to study drug, will be followed by the Investigator until resolution or stabilization. Clinical, laboratory, and diagnostic measures should be employed by the Investigator as needed to adequately determine the etiology of the event.

10.3.5.4 *Serious Adverse Event Reporting*

10.3.5.4.1 Reporting Requirements

Any AE that meets SAE criteria must be reported to the Sponsor and/or designee immediately (i.e., within 24 hours) after the time site personnel first learn about the event using the SAE Report Form provided for the study. Regardless of causality, all SAEs must be reported and will be collected and recorded from the time the participant/legal guardian signs the ICF until completion of the final follow-up visit. All SAEs must also be recorded in the participant's source documentation and on the AE page of the participant's eCRF.

The initial report should include at least the following information:

- Study number
- Participant's identification number
- Description of the event
- Date and time of onset of the event
- Seriousness criteria
- Causality assessment to study drug

If follow-up is obtained or requested by the Sponsor and/or designee, the additional information should be emailed on an SAE Report Form to the Sponsor in a timely manner according to the procedures and timelines outlined above. Copies of discharge summaries, consultant reports, autopsy reports, and any other relevant documents may also be requested.

The Investigator will be responsible for reporting all SAEs to the IRB or EC. The Sponsor will be responsible for reporting to the regulatory authorities and Central Ethics Committees, as per local requirements.

An Investigator who receives an Investigator Safety Report describing an SAE or other specific safety information (e.g., summary or listing of SAEs) from the Sponsor will review and file it along with the IB and will notify the IRB/EC, if appropriate according to local requirements.

